#### **8.Data and Safety Monitoring:**

Describe plans for data and safety monitoring to ensure the safety of subjects and the quality of the data. As described in federal guidance "... a variety of types of monitoring may be anticipated depending on the nature, size, and complexity of the trial. In many cases, the principal investigator would be expected to perform the monitoring function." This plan should include monitoring to determine:

The progress of the trial, including periodic assessments of data quality and timeliness, participant recruitment, accrual and retention, participant risk versus benefit, and other factors that can affect study outcome. Monitoring should also consider factors external to the study when interpreting the data, such as scientific or therapeutic developments that may have an impact on the safety of the participants or the ethics of the study.

Note: This section does not request information related to sponsor study monitor visits. This section requires a description of an adequate data and safety monitoring plan.

The safety of dual macro-micro electrodes will be assessed with every patient. Complete data analysis will be done with every patient.

#### **9.Genetics:**

Does any part of the study involve genetic analysis of biological specimens?

Yes  No

If yes, respond to **Genetics Attachment C**

#### **10.Instruments:**

Describe each instrument, if any, used to collect data in this study.

Attach copies of any questionnaires, surveys, or interview questions. If the research involves interviews that could evolve as the research progresses, include a list of discussion topics and any "starter" questions for each topic that can reasonably be expected to be covered. If a draft of a written questionnaire or survey is attached, it should be clearly labeled as such and a final version should be sent to Dartmouth-Hitchcock Health (D-HH) IRB for review before data collection begins.

#### **11.Deception:**

Will deception of participants, including withheld information, be used in this research?

Yes  No

If yes, complete a-d.

**a)** Describe the deception being used in this study:

**b)** Explain why deception is necessary in this research:

**c)** Describe the information provided to subjects when they decide to participate:

**d)** Describe how the subjects will be provided with additional pertinent information after participation (debriefing):

## **12. Timetables:**

**a)** Indicate length of participant involvement in the study: **Each participant will be enrolled into the study for the duration of their iEEG monitoring, this is an inpatient admission of less than two weeks.**

**b)** Estimate how long it will take to enroll enough participants to complete this study: **This will be an ongoing study. We think we can enroll 2-3 patients per year.**

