**7. Statistical Methods and Review Statement:**

**a)** Specify the primary endpoint, as well as other endpoint(s).

The primary hypothesis is that high oscillations (fast ripples) occur in epileptogenic cortex and are absent in non-epileptogenic cortex. Our secondary hypothesis is that single unit activity recorded from various electrode positions in the brain will correlate with specific cognitive tasks.

**b)** State the statistical analysis plan, including all hypothesis tests (e.g., t-test, chi-square), and estimation methods related to the primary endpoint. If a formal protocol for the study exists, page references to the protocol are acceptable.

The recording of high frequency oscillations will require only basic statistical analysis using chi-square testing. The analysis of neuronal discharge characteristics and temporal association with specific cognitive tasks will be done using Matlab.

**c)** Justify the sample size, using the concepts of power, type I error, and effect size if applicable. If a formal protocol for the study exists, page references to the protocol are acceptable.

We are planning to enroll up to 50 patients over an extended period of time. The power calculations and effect size, will depend on the cognitive task applied in the individual patient for the specific electrode array.

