**16. Adequacy of Resources to Protect Subjects:**

**a)** Investigator (including co-investigators) has sufficient time to conduct and complete the research.

Yes  No

**b)** Adequately qualified (including experience, training, supervision, and familiarity with the protocol) staff are available for this research.

Yes  No.

**c)** Describe availability of psychological, social, or medical services, which include counseling or social support services, that may be required as a consequence of research participation.

Patients are routinely evaluated by neuropsychologists as part of routine work-up. As subjects will be inpatients during their participation in the study, epilepsy, neuropsychiatry, and psychology services will be available.

**d)** Describe psychological, social, or medical monitoring, ancillary care, equipment needed to protect participants (e.g. close proximity to resuscitation equipment or a plan for monitoring of emotional state during study procedures).

The study will be conducted inside the Epilepsy Monitoring Unit (EMU) at DHMC. This unit is specifically equipped to deal with complications of epilepsy and epilepsy surgery. The unit has continuous video EEG monitoring, meets safety standards for operating an EMU, has specially trained and qualified nurses who are able to treat seizures.

e) Describe other resources needed for the protection of subjects in the conduct of this research (e.g. language translation services).

None

**f)** Explain how the investigator has access to a population that would allow recruitment of the required number of subjects.

Patients who have medically refractory epilepsy are referred to the DHMC Epilepsy Center for surgical evaluation. Each year, between 10-15 intracranial EEG studies are performed. Patients will be recruited from among all patient who meet the inclusion criteria. We anticipate that 5-8 patients per year will be recruited to participate in the study.

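### Do the two accrual forecasts, 2-3 and 5-8 patients per year, undermine the planned size of up to 50?

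*Combined protocol and SAP*

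**What the plan says.** Three items of the combined protocol and SAP bear on accrual.

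- Section 7 (Statistical Methods and Review Statement), item c, gives the size: "We are planning to enroll up to 50 patients over an extended period of time". It offers no alpha, power or effect size, and says instead: "The power calculations and effect size, will depend on the cognitive task applied in the individual patient for the specific electrode array".
- Section 12 (Timetables), item b, asks how long enrolment will take. The answer gives no duration. It says "This will be an ongoing study" and adds "We think we can enroll 2-3 patients per year".
- Section 16 (Adequacy of Resources to Protect Subjects), item f, asks how the investigator has access to enough patients. The answer gives the source population, "Each year, between 10-15 intracranial EEG studies are performed", and the expected yield, "We anticipate that 5-8 patients per year will be recruited to participate in the study".

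Section 15 lists one site. No section sets a minimum number of patients, an accrual period or an analysis date.

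**The concern.** The two forecasts cannot both be right. They concern one study at one site, and the top of the lower range (3 per year) is below the bottom of the higher range (5 per year). Section 16f cannot be read as counting patients merely approached, because it speaks of patients recruited to take part.

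The figure of up to 50 is the only quantitative planning figure in section 7, so a reader naturally turns to accrual to learn what the study will yield. At the lower rate, 50 patients would take about two decades. The study would then probably be reported on far fewer patients than a reader of section 7 might suppose, with less precision on the primary fast-ripple question. Because the study is open-ended, there is also a worry that the stopping point could be chosen after the data have been seen.

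**Working it through.** **Inputs.** Upper limit of 50 patients (section 7c). Accrual of 2-3 per year (section 12b) or 5-8 per year (section 16f). Source population of 10-15 intracranial EEG studies per year (section 16f). No duration is stated.

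**Can the figure of 50 be reproduced?** No. With no alpha, power, effect size or event rate, there is no calculation to repeat. The accrual rates are not used to derive it either.

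**Time to 50 = 50 / annual rate.**

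| Source | Rate per year | Years to 50 |
|---|---|---|
| Section 12b | 2 | 50/2 = 25 |
| Section 12b | 3 | 50/3 = 16.7 |
| Section 16f | 5 | 50/5 = 10 |
| Section 16f | 8 | 50/8 = 6.25 |

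The slowest and fastest cases differ by a factor of 25/6.25 = 4.

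**Share of the source population = annual rate / annual intracranial EEG studies.**

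- Section 12b: from 2/15 = 13% to 3/10 = 30%.
- Section 16f: from 5/15 = 33% to 8/10 = 80%.

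Both rates fit within the available patients. The documents therefore rule out neither, and do not show which is the better forecast.

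**What would be lost under slow accrual (illustration only).** Assume a ten-year horizon, which the documents do not state. Enrolment is then 2 × 10 = 20 to 3 × 10 = 30 under section 12b, and 5 × 10 = 50 to 8 × 10 = 80 under section 16f, where the limit of 50 would apply.

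Assume further that each patient gives one independent observation from non-epileptogenic cortex and that none shows fast ripples. The one-sided 95% upper bound for the true proportion is 1 − 0.05^(1/n):

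- n = 20: 1 − 0.05^(1/20) = 13.9%
- n = 30: 1 − 0.05^(1/30) = 9.5%
- n = 50: 1 − 0.05^(1/50) = 5.8%

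These bounds give a sense of scale, but they do not describe a planned analysis. Section 7b specifies chi-square testing for the oscillations, and the primary hypothesis compares epileptogenic with non-epileptogenic cortex. The plan nowhere proposes a per-patient, zero-event proportion.

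**Does any stated quantity depend on the rate?** Going through the items in turn:

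- Section 7a (hypotheses): no.
- Section 7b (tests): no.
- Section 7c (upper limit): no, since a limit is respected at any rate.
- Section 12a (each patient's time in the study): no.
- Section 12b (duration): none is given, so none is contradicted.

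**The case for a change.** The best case for a change runs as follows. The form asks in section 12b how long enrolment will take and in section 16f whether enough patients are available. The first answer gives no duration, and the second rests on a rate that the first contradicts. The feasibility statement put to the ethics committee is therefore unsupported as written. Section 7c defers power to the cognitive task, which belongs to the secondary hypothesis, so accrual is the only guide to what the primary question will receive. Section 8 promises a complete analysis with every patient; without an end date, the final number could be chosen in the light of results. Putting this right would take a few sentences.

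Part of this stands. The contradiction is real, the divisions are correct, and a reader cannot tell from the plan when 50 would be reached.

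The rest does not follow from the mismatch:

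- The phrase about a required number in section 16f belongs to the form's printed prompt. The investigators never describe 50 as required; they give it as an upper limit, so asking for 50 to be treated as a cap asks for what is already written.
- To conclude that 50 cannot be delivered, one must take the lower rate as true and supply a deadline. The documents do neither.
- The worry about a data-driven stopping point comes from having no fixed analysis date. It would be just as strong if sections 12b and 16f agreed, so it is a separate question. Setting a calendar date for an open-ended, exploratory study is a debatable design choice that this mismatch does not justify.
- The lack of a stated precision for the expected number is missing detail in section 7c. It would remain under either rate.

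**Conclusion.** The forecasts of 2-3 and 5-8 patients per year are inconsistent, and the time to 50 is indeterminate between about 6 and 25 years. No change to the statistical plan follows. Fifty is a cap without a deadline, no minimum is set, and neither rate enters a power calculation, a test or a decision rule. Whichever forecast is right, the same analyses would be run on the patients enrolled, and a report would give the number reached and the precision it supports. Harmonising the two answers would tidy the form but would alter no result or conclusion.

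This rests on reading section 7c as a ceiling and section 12b as open-ended, which is what their wording says. It would be different if the plan elsewhere committed to 50 as a target, to a closing date, or to a power statement that needed 50; it does none of these. The ten-year totals and the bounds of 13.9%, 9.5% and 5.8% depend on assumptions from outside the plan and carry no weight in this conclusion.

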## **13. Risks:**

The purpose of this section is to determine if subjects will be placed "at risk," which in general means exposed to the possibility of physical, psychological, social, economic, legal, dignitary or other harm as a consequence of any activity proposed in the research project.

**a)** What is the overall risk classification of the research?

- Minimal
- Greater than minimal
- Significant
- Unknown

Note: In the federal regulations on human subjects protection minimal risk means "The probability and magnitude of harm or discomfort anticipated in the research are not greater in and of themselves than those ordinarily encountered in daily life or during the performance of routine physical or psychological examinations or tests."

**b)** Describe any potential risks (physical, psychological, social, legal, economic, or other) and assess their likelihood and seriousness. Describe the procedures for protecting against or minimizing these risks, including risks to confidentiality, and assess their likely effectiveness. Please list risks from most severe/likely to least severe/unlikely.

The risk of participation in the study overall is only minimally greater than standard iEEG recording, although conclusive risk assessment is not available. The safety of dual micro-macro electrode systems has been analyzed in a retrospective study done at the Mayo Clinic by Van Gompell et al. In this study, 24 consecutive patients underwent long-term iEEG monitoring with implanted dual depth and subdural grid and strip electrodes; both clinical macroelectrodes and research microelectrodes were used. The patients included 18 women and 6 men with an average age of 35 (range 21–65). The mean hospital stay was 11 days (range 5–20), with mean duration of implantation 7.0 days (range 3–15). Data from the 198 consecutive craniotomies for standard clinical subdural grid insertion (prior to surgery in the 24 patients described here) were used for comparison to investigate the relative risk of complications. The overall complication rate was 4.2% (only 1 patient had a complication), which did not significantly differ from the complication rate previously reported by the authors of 6.6% when standard subdural and depth intracranial electrodes were used. There were no deaths or permanent neurological deficits related to electrode implantation. In conclusion, the authors demonstrated the use of hybrid subdural strip and grid electrodes containing standard clinical macroelectrodes. In this initial study in 24 patients, the complication rate is acceptable, and there does not appear to be increased risk associated with the use of hybrid electrodes compared with standard subdural and depth iEEG electrodes. Please refer to Attachments #1 and #2 for further details.

Digital Lynx system is not FDA approved. However, it has been certified to be UL/EN 60601-1 and 60601-22 compliant. Details are enclosed in attachment #3.

A theoretical risk of potential physical neuronal injury by direct contact of a microelectrode with a neuron exists. This type of injury has not been reported in humans with use of microelectrodes. Potential injury by direct microelectrode contact would most likely be limited to single neurons or very small populations of neurons. No neurocognitive effect would be expected by injury to such small populations of neurons.

#### **14. Risk/Benefit analysis:**

Describe why the risks to subjects are reasonable in relation to the anticipated benefits to participants and in relation to the importance of the knowledge that may reasonably be expected to result from the study.

The potential risk of this study is reasonable given the wealth of potential information which may be gained from this study. Potential benefits include improvement in prediction of neuropsychological outcomes, improvement in detection of epileptogenic brain regions, and novel understanding of neurocognitive mechanisms.

#### **15. Research Setting**

a) Is this a multi-center study?

Yes  No

If yes: Are you the lead investigator?  Yes  No

If you are NOT the lead investigator:

Name of lead investigator:

Institution where the lead investigator is located:

**b)** List all sites where research will take place and D-HH is the reviewing IRB (e.g. DHMC Alliance Hospitals, DHMC Clinics, WRJ VAMC):

DHMC - Lebanon

**c) If you are the lead investigator of a multi-center study, list all sites where research will take place and D-HH is NOT the reviewing IRB:** or check  *N/A*

Note: Each site taking part in the research should have appropriate institutional or IRB oversight. A Site Agreement or Federalwide Assurance may be required. The D-HH office can assist you with these arrangements.

**d) Does the study involve sites outside of the United States and Canada?**

Yes  No

If yes, are arrangements for the international site(s) being made by a multinational pharmaceutical or device sponsor or a cooperative oncology working group?

Yes  No

If no, please **complete Attachment L**.

**16. Adequacy of Resources to Protect Subjects:**

**a)** Investigator (including co-investigators) has sufficient time to conduct and complete the research.

Yes  No

**b)** Adequately qualified (including experience, training, supervision, and familiarity with the protocol) staff are available for this research.

Yes  No.

**c)** Describe availability of psychological, social, or medical services, which include counseling or social support services, that may be required as a consequence of research participation.

Patients are routinely evaluated by neuropsychologists as part of routine work-up. As subjects will be inpatients during their participation in the study, epilepsy, neuropsychiatry, and psychology services will be available.

**d)** Describe psychological, social, or medical monitoring, ancillary care, equipment needed to protect participants (e.g. close proximity to resuscitation equipment or a plan for monitoring of emotional state during study procedures).

The study will be conducted inside the Epilepsy Monitoring Unit (EMU) at DHMC. This unit is specifically equipped to deal with complications of epilepsy and epilepsy surgery. The unit has continuous video EEG monitoring, meets safety standards for operating an EMU, has specially trained and qualified nurses who are able to treat seizures.

e) Describe other resources needed for the protection of subjects in the conduct of this research (e.g. language translation services).

None

**f)** Explain how the investigator has access to a population that would allow recruitment of the required number of subjects.

Patients who have medically refractory epilepsy are referred to the DHMC Epilepsy Center for surgical evaluation. Each year, between 10-15 intracranial EEG studies are performed. Patients will be recruited from among all patient who meet the inclusion criteria. We anticipate that 5-8 patients per year will be recruited to participate in the study.

### **17. Participant Population:**

Certain populations are considered vulnerable to coercion and undue influence. These populations are provided with additional protections when participating in a research study. The populations include:

- prisoners
- human embryos
- fetuses
- elderly people
- people with an cognitive disability (also see #23 below)
- people with a disabling psychiatric illness
- people who are economically disadvantaged persons
- people who are illiterate

Refer to: Students, Employees **Attachment D**  
Illiterate Subjects **Attachment E**

a) List vulnerable groups: \_\_\_\_\_ or check  *None*

People with a cognitive disability who meet the inclusion criteria, and are capable of performing the cognitive tasks, but are not capable of giving informed consent.

**b)** Describe additional protections: \_\_\_\_\_ or check  N/A

The informed consent process for potential participants with a cognitive disability who have a legal guardian will include the participant and their legal guardian. As the risks associated with this study are minimal, no other additional protections would be needed.

## **18. Gender and Racial/Ethnic distribution:**

NIH guidelines state that research involving human participation should include minorities and both genders.

Note: If one gender or minorities are excluded or are inadequately represented in this research, particularly in proposed population-based studies, a clear and compelling rationale for exclusion or inadequate representation should be provided.

Will eligibility for the study be based on gender, race, or ethnicity?  Yes  No  
If yes, explain:

**19. Pregnant Women:**

Are pregnant women eligible for enrollment into this study?  Yes  No  
If yes, respond to **Research Involving Pregnant Women, Fetuses and Neonates: Attachment M**  
If no, explain and include a process to determine pregnancy status. If a pregnancy test is required, note who will pay:

**20. Fetuses and Neonates:**

Are fetuses and neonates participants in the research?

Yes  No

If yes, respond to **Research Involving Pregnant Women, Fetuses and Neonates: Attachment M**

**21. Children:**

Are children eligible for enrollment into this study? Under state law, a child is a person less than 18 years old.

Yes  No

If yes, respond to **Children: Attachment F**

If no, present an acceptable justification for the exclusion:

Note: NIH guidelines state that research involving human participation should include children unless there is appropriate justification for their exclusion. The investigator should address the rationale for selecting or excluding a specific age range of children, or an explanation of the reasons for excluding children as participants in the research. When children are included, the plan should also include a description of the expertise of the investigative team for dealing with children at the ages included, of the available facilities to accommodate the children, and a sufficient number of children to contribute meaningfully to the study analysis.

**22. Women of Child-Bearing Capability**

Are women of child-bearing capability eligible for enrollment into this study?

Yes  No

If yes, describe potential harm to an unborn fetus from study activities and the process for determining pregnancy status if necessary. If a pregnancy test is required, note who will pay. If there is potential harm to an unborn fetus, the investigator should review with each individual a plan to avoid pregnancy. If the investigator regards these contraceptive plans as inadequate, the individual should be advised on how to achieve adequate contraception or should be excluded from the study.

All patients undergoing surgical work up for epilepsy have a pregnancy test done. Patients who are pregnant are excluded from epilepsy surgery and will not be included in this study.

If no, explain why this population is not eligible and how you will determine eligibility for each woman.

